### 3.3 DOSE MODIFICATIONS

#### 3.3.1 GENERAL GUIDANCE

Vandetanib should be held for any treatment-limiting toxicity (see Section 3.1.2). For treatment limiting toxicities that include a duration in the definition, such as a neutrophil count below 1,000/ $\mu$ L (grade 3) on 2 consecutive measurements drawn at least 72 hours, the drug will be held after the toxicity reaches the grade defined in treatment limiting (e.g., after the second ANC <1,000/ $\mu$ L).

If vandetanib-related treatment-limiting toxicity resolves to grade  $\leq$ 1 or baseline in  $\leq$ 6 consecutive weeks of drug free period, vandetanib may be restarted at a reduced dose.

If the vandetanib-related treatment-limiting toxicity does not resolve to grade  $\leq 1$  or baseline in  $\leq 6$  consecutive weeks of a drug free period the patient should discontinue protocol therapy and be monitored until the toxicity resolves.

The cycle duration remains 28 consecutive days in patients who have dose interruptions.

If a patient happens to miss 6 weeks of dosing for non-toxic events, if monitoring is initiated as described in Section 3.5.1, the patient may initiate re-dosing.

Refer to Section 4 Concomitant Medications/Measures for management of specific toxicities.

Refer to Section 3.1.1 for intra patient dose escalations.

### 3.3.2 DOSE MODIFICATION RULES

The NCI Principal Investigator should be consulted for all dose reductions. Dose modifications will be conducted according to the following guide:

- Patients who experience a treatment-limiting toxicity (Section 3.1.2) that is possibly, probably, or definitely related to vandetanib should have a dose reduction of their vandetanib dose after recovery from toxicity (to a CTCAE Grade 1 or baseline) (Section 3.2 Drug Administration) following the table below for the remainder of the current course and for the subsequent cycles of treatment.

Vandetanib starting dose (mg/dose) once daily	Dose reduction (mg/dose)	Dose reduction (%)
50	50 mg 5 times/week (e.g. Monday, Tuesday, Thursday, Friday, Sunday)	29%
100	100 mg 5 times/week (e.g. Monday, Tuesday, Thursday, Friday, Sunday)	29%
150	100 daily	33%
200	200 mg 5 times/week (e.g. Monday, Tuesday, Thursday, Friday, Sunday)	29%
250	200 mg 6 times/week (Monday, Tuesday, Wednesday, Thursday, Friday, Saturday)	40%
300	200 daily	33%

- Patients who experience treatment-limiting toxicity after a dose reduction can have one additional dose reduction. All dose reductions should be approximately 30% of the administered dose. The protocol PI or lead AI should confirm the dose reduction.

- Patients who have a dose reduction for a non-life-threatening treatment-limiting toxicity (diarrhea, nausea, vomiting, constipation, anorexia, weight loss, fatigue or skin rash) and who tolerate  $\geq 2$  cycles at the reduced dose can have their dose re-escalated to the prior dose level. The toxicity type that was previously treatment-limiting toxicity at the higher dose level must not have exceeded grade 1 at the reduced dose level in order to re-escalate the dose.

### 3.3.3 DOSE MODIFICATION TO PROMOTE WOUND HEALING

- Subjects who require **elective surgery**, vandetanib should be held for 2 weeks prior to the procedure and for 2 weeks after surgery. The treatment should resume only after the surgeon has determined that the wound is healed. Subjects should have restaging studies performed prior to restarting the treatment.
- Subjects who require **emergency surgery or who experience a significant injury**, the vandetanib should be held for at least 2 weeks and only resumed when the wounds are judged to be healed. If the vandetanib is held for 4 or more weeks, then restaging studies should be performed prior to restarting the treatment.

## 3.4 QUESTIONNAIRES

As described in [Section 1.2.3](#), the pediatric PROMIS instruments and the Distress Rating Tool will be administered to all consenting patients who speak English or Spanish with parallel Parent Proxy instruments administered to parents of patients ages 8-17. These instruments will be administered at baseline, at the first re-staging visit (3 months) and at the time a patient is taken off treatment (See [Appendix 12](#), [Appendix 13](#), and [Appendix 14](#)). Since the measures have not been validated in other languages, participation in this portion of the study will be limited to subjects who speak either English or Spanish.

## 3.5 STUDY CALENDAR

See [Appendix 9](#).

Subjects will be monitored according to study requirements, including history and physical examinations, blood pressure monitoring, performance status, urinalysis and routine laboratory tests (blood counts and chemistries), as per [Appendix 9](#).

### 3.5.1 MONITORING DURING DRUG THERAPY

#### 3.5.1.1 Blood Pressure

Blood pressure should be monitored and recorded prior to the first dose of vandetanib, and with physical exams during cycle 1. In addition, blood pressure should be monitored and recorded cycle 1, day 14, prior to each cycle on cycles 2, 3, 4, then every 3 cycles (prior to cycle 7, 10, 13, etc). See [Appendix 2](#) for management of elevated diastolic BP.

#### 3.5.1.2 Physical Examination:

A physical examination should be performed at Day 14 during cycle 1. Then prior to cycle 2, 3 and 4; then every 3 cycles prior to cycle 7, 10, 13, etc.

3.5.1.3 Height, Weight, and BSA:

Recorded prior to the first treatment and then on each restaging cycle (cycle 4, 7, 10, 13, and then every 6 cycles, i.e. prior to cycle 19, 25, 31, etc.).

3.5.1.4 Performance Status:

Record prior to the first treatment cycle and then on each restaging cycle (cycle 4, 7, 10, 13, and then every 6 cycles, i.e. prior to cycle 19, 25, 31, etc.) ([Appendix 1](#)).

3.5.1.5 Laboratory

3.5.1.5.1 Hematology:

Complete blood count, differential and platelet count on Day 14 (more frequent monitoring may be performed if the ANC <1,000/ $\mu$ L or platelet count <50,000/ $\mu$ L) for cycle 1, and then prior to cycle 2, cycle 3 and cycle 4; then every 3 cycles prior to cycle 7, 10, 13, etc.

3.5.1.5.2 Chemistries:

On Day 14: BUN, creatinine, electrolytes (including (sodium, potassium, chloride, CO2)), LDH, AST, ALT, alkaline phosphatase, bilirubin (total and direct if total is elevated), calcium, magnesium, phosphorus, glucose, and uric acid during cycle 1, and then prior to cycle 2, 3, and 4. Then every 3 cycles prior to cycle 7, 10, 13, etc.

3.5.1.5.3 Thyroid Stimulating Hormone:

Prior to cycle 2, 3 and 4; then every 3 cycles i.e. cycle 7, 10, 13, etc. If TSH is abnormal, T4 will be evaluated.

3.5.1.5.4 Urinalysis:

Prior to cycle 2, 3 and 4; then every 3 cycles i.e. cycle 7, 10, 13, etc.

3.5.1.5.5 Serum/Urine Pregnancy Test:

Prior to the first cycle in females with child bearing potential, and then prior to cycles 4, 7, 10, 13, then every 6 cycles (19, 25, 31, etc).

3.5.1.6 ECG with Calculation of QTc

Prior to cycle 1, 2, 3 and 4; then every 3 cycles i.e. cycle 7, 10, 13, etc. See [Section 4](#) for management of QTc prolongation.

Use Bazett's correction ( $QTcB = QT/RR^{0.5}$ ).

3.5.1.7 A unilateral knee MRI:

Will be performed in all patients with open growth plates on lower extremity scanogram (See [Appendix 11](#)). Repeat knee MRIs will be performed every 3 cycles x 4 (prior to cycle 4, 7, 10, 13) and then every 6 cycles (prior to cycle 19, 25, 31, etc) until growth plates are fused.

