# 3 STUDY IMPLEMENTATION

## 3.1 STUDY DESIGN

### 3.1.1 STUDY OVERVIEW

This phase II trial is designed to determine whether daily oral vandetanib is active (clinical activity as per RECIST v1.1) in patients with wt- GIST. Vandetanib activity will be primarily assessed by response of measurable disease using RECIST (v1.1), but change in tumor-related symptoms from baseline will also be monitored to assess drug effect.

Adults and children (patients older than 3 years) with measurable wt-GIST will be eligible for trial participation. Patients must have measurable disease by RECIST and adequate organ function.

Vandetanib will be administered orally once a day on a continuous dosing schedule. One treatment cycle equals 28 days.

- Patients 18 years and older at the time of enrollment on this study will start vandetanib at a fixed dose of 200 mg once daily (QD) for cycles 1, 2, and 3.

- Patients younger than 18 years of age at the time of enrollment will start vandetanib at a dose of 100 mg/m^2/dose for cycles 1, 2 and 3. (see table below).

Table 1: Vandetanib Dose Escalation Schedule	
Age at Enrollment	Daily Dose of Vandetanib
Patients < 18 years of age	Cycles 1-3: 100 mg/m  /dose
	If vandetanib is well tolerated : Cycles ≥4: 150 mg/m  /dose
Patients ≥ 18 years of age	Cycles 1-3: 200 mg/dose
	If vandetanib is well tolerated : Cycles ≥4: 300 mg/dose

A one time intra patient dose escalation to 150 mg/m^2/dose for patients < 18 years, and to 300 mg/dose for patients ≥ 18 years will be allowed after completion of 3 cycles, provided provided the intra patient dose escalation criteria below are fulfilled:

Vandetanib is well tolerated at the starting dose defined as:

- All vandetanib related toxicities during cycle 1-3 are less than grade 2, except grade 2 toxicities that are:
  - isolated laboratory abnormalities and not present at repeat blood draw, or
  - short lived and resolve within approximately 72 hours with or without supportive therapy.

There is no limit on the number of cycles that a patient may receive. The dosing nomogram provided in section 3.2 will be used to determine the vandetanib dose for pediatric patients.

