- During the QTcB prolongation period: For a single QTcB value of >500 ms, vandetanib must be withheld. Electrocardiograms will be followed at least once per week (done at the same day each week) along with electrolytes, until QTcB falls  $\leq 480$  ms. Vandetanib treatment may be resumed at a permanently lower dose after the QTcB returns to  $\leq 480$  ms.

Treatment-limiting QTc prolongation is defined as a single QTc value  $\geq 500$  msec. Post the QTcB prolongation period: If vandetanib (at the reduced dose) is restarted after the QTcB prolongation has resolved, ECGs and electrolytes (including potassium, calcium and magnesium) must be obtained at 3, 8, and 12 weeks following the start of the lower dose. Serum potassium levels should be maintained at 4 mEq/L or higher, and serum magnesium and serum calcium should be kept within normal range to reduce the risk of QT prolongation. ECG and electrolyte monitoring can then resume every 3 weeks at the normal visit schedule for the patient.

If a patient is on 100 mg vandetanib dose and has QTcB >500 ms, vandetanib 100 mg may be given every other day.

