## **10.4 EVALUATION OF BENEFITS AND RISKS/DISCOMFORTS**

### **10.4.1 RISKS OF VANDETANIB**

The primary risk to patients participating in this research study is from toxicity of vandetanib. In adults, vandetanib has been relatively well tolerated. The most common adverse events have been rash, diarrhea and asymptomatic QTc prolongation, which are reversible and generally can be alleviated by dose reduction. In the ongoing NCI protocol 07-C-0189 the most common toxicities in children have been diarrhea, rash, and TSH elevation. The response rate in subjects with wt-GIST is unknown, but vandetanib has shown clinical activity in MTC. A complete summary of Vandetanib risks is contained in Section 11.1.6.

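### Scheduled ECG, chemistry and blood pressure checks move to every 12 weeks at the cycle in which the dose may be raised, and the protocol does not say what monitoring follows an increase

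*Combined protocol and SAP*

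**What the plan says.** **Dose.** Section 3.1.1 defines the cycle ("One treatment cycle equals 28 days") and permits a single increase within a patient, which "will be allowed after completion of 3 cycles" if the tolerance criteria are met. For adults, Table 1 reads "If vandetanib is well tolerated : Cycles ≥4: 300 mg/dose", up from 200 mg; for patients under 18 the step is from 100 to 150 mg/m². The arms table in section 2.4 lists the same cycle 4 doses without the tolerance condition.

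**Scheduled checks.**
- ECG (3.5.1.6): "Prior to cycle 1, 2, 3 and 4; then every 3 cycles i.e. cycle 7, 10, 13, etc".
- Chemistries, including potassium, calcium and magnesium (3.5.1.5): day 14 of cycle 1, before cycles 2, 3 and 4, and "then every 3 cycles prior to cycle 7, 10, 13, etc".
- Blood pressure (3.5.1.1): before the first dose, day 14 of cycle 1, and "prior to each cycle on cycles 2, 3, 4, then every 3 cycles (prior to cycle 7, 10, 13, etc". Appendix 4 repeats this pattern for adults.
- Appendix 9, so far as its table can be read, agrees with 3.5.1.

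**After a dose reduction for QTc prolongation.** Section 3.1.2 says that ECGs and electrolytes "must be obtained at 3, 8, and 12 weeks following the start of the lower dose". It then says monitoring may go back to a three-week interval, which it describes as the patient's usual visit schedule.

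**After a dose increase.** No section mentions monitoring.

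**The concern.** The last of the four-weekly checks is the one before cycle 4, so it is taken on the starting dose. The next scheduled one falls 12 weeks into the higher dose. Section 10.4.1 lists "rash, diarrhea and asymptomatic QTc prolongation" as the most common adverse events in adults, and 3.1.2 defines treatment-limiting QTc prolongation by a single ECG value. A change without symptoms that follows the increase would then have no scheduled opportunity to be found for almost three months.

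Two things are at stake. The first is patient safety during that interval, made less clear by two incompatible statements of the ordinary ECG and electrolyte schedule. The second is how the safety data are read. Objective 1.1.2.1 is to assess safety and toxicity at established doses, and section 8.2 summarises adverse events without reference to the dose being taken. Fewer ECG, laboratory or blood pressure findings at the higher dose could reflect fewer checks.

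**Working it through.** No figure in the plan can be reproduced here; the check is arithmetic on the visit schedule.

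**Inputs.** Cycle length 28 days (3.1.1). Check times from 3.5.1.1, 3.5.1.5 and 3.5.1.6. Increase at the start of cycle 4 (3.1.1). Restart checks from 3.1.2.

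**Formula.** Day of the visit before cycle c = (c − 1) × 28.
- Cycles 2, 3, 4: days 28, 56, 84 (weeks 4, 8, 12).
- Cycle 7: 6 × 28 = day 168 (week 24).
- Time from the increase to the next scheduled check: 168 − 84 = 84 days. The ±7-day window that Appendix 9 allows from cycle 5 on could extend this to 91.

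**Scheduled on-treatment checks in the first 84 days of each period.**

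| Period | ECG | Electrolytes | Blood pressure |
|---|---|---|---|
| Starting dose | 3 (weeks 4, 8, 12) | 4 (weeks 2, 4, 8, 12) | 4 (weeks 2, 4, 8, 12) |
| After the increase | 1 (week 12) | 1 (week 12) | 1 (week 12) |
| Restart at a reduced dose after QTc prolongation | 3 (weeks 3, 8, 12) | 3 (weeks 3, 8, 12) | no fixed schedule stated |

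The escalated period therefore has one third of the ECGs and one quarter of the electrolyte and blood pressure checks, all at its end.

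**Size of the step.** Nominally 300/200 − 1 = 50% in adults and 150/100 − 1 = 50% in children. With the nomogram in 3.2, the change in a child's daily dose ranges from none (BSA 0.75–0.83 m², 100 mg at both levels) to a doubling (0.50–0.74 m², 50 to 100 mg; 1.17–1.24 m², 100 to 200 mg).

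**The two statements of the usual schedule.** Under 3.5.1, ECG and electrolytes fall every 4 weeks and then every 12. Under the closing sentence on restart in 3.1.2, they fall every 3 weeks, which is 12/3 = 4 per 12 weeks. Depending on which governs, the first 12 weeks at the higher dose hold one ECG or four. The 3.1.2 sentence does not cover blood pressure, so the 84-day blood pressure interval stands either way.

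**Unscheduled checks.**
- 3.1.2: extra ECGs once prolongation is found.
- 4.1.4: regular QTcB and electrolyte checks if a restricted co-medication is used.
- 4.5 and 4.5.2: electrolytes with vomiting or diarrhea.
- Appendix 4: more frequent blood pressure in adults whose raised pressure needs medication.
- 3.5.1.8 and Appendix 8: a daily diary until cycle 13, with instructions to report symptoms such as irregular heartbeat or dizziness.

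Each starts from a detected abnormality, a symptom or a co-medication. None is triggered by the increase itself.

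**The case against.** The strongest reply is that the schedule follows time on treatment, not dose. Patients who are not escalated move to the same 12-week interval. Those who are escalated have just completed three cycles with related toxicity below grade 2, apart from narrow exceptions. Section 7.5 relies on a well-established toxicity profile, and section 1.2.2.1 reports pediatric use at 150 mg/m² without cumulative toxicity. Less frequent monitoring in such patients can be a deliberate choice. That stands as a reason for the general thinning. It does not answer why a dose change goes unmentioned in the monitoring plan, and it leaves the conflict between 3.1.2 and 3.5.1 untouched.

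Four stronger readings are tempting, and the documents do not support them:
- *A step down is watched more closely than a step up.* The 3-, 8- and 12-week checks apply only to a restart after QTc prolongation, and only to ECG and electrolytes. Other reductions in 3.3.2 carry no added ECGs. Closer follow-up of patients who have had a treatment-limiting QTc is a risk-based choice.
- *Extra ECGs occur only after prolongation is seen.* Section 4.1.4 also requires QTcB checks with certain co-medications.
- *The 300 mg rates in section 11.1.6 (QT prolongation 7.5%, hypertension 22.4%) give the number harmed.* They are overall percentages on 300 mg monotherapy. They do not measure the increment from 200 to 300 mg and do not come from patients selected for tolerance.
- *A planned comparison between doses is biased.* Section 8.2 plans none. The risk lies in interpretation, mainly for findings that need a test; symptomatic events are also recorded in the diary.

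**Conclusion.** The point holds for patients who meet the escalation criteria. Under 3.5.1 and Appendix 9, their first scheduled ECG, electrolyte and blood pressure check on the higher dose falls 84 days after the increase: one ECG against three, and one electrolyte and blood pressure check against four, in the first 12 weeks of each dose. The protocol does not say what monitoring follows an increase, and it contradicts itself on the ordinary ECG and electrolyte interval.

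This assumes that the increase takes effect at the start of cycle 4 and that 3.5.1 governs over the passing reference in 3.1.2. If 3.1.2 governs, the ECG and electrolyte gap closes but the blood pressure gap remains. The documents do not allow an estimate of how many events would be missed. Section 8.3 records that accrual closed after nine patients and does not say how many may still be escalated, so the calendar change may reach few of them. The tabulation applies to whatever data have been collected.

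**What to change.** 1. Reconcile sections 3.1.1, 3.1.2, 3.5.1 and Appendix 9 so that a single ordinary ECG and electrolyte schedule applies, and so that the protocol states which ECG, electrolyte and blood pressure monitoring applies after a dose increase. The clinical team decides content and timing; no schedule is proposed here.
2. In section 8.2, add a tabulation of adverse events by the dose being taken at onset, with time on each dose and the number of scheduled checks at each dose. Fewer detected events at the higher dose would then not be read as better tolerance.

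Cost: a calendar amendment, possibly a few routine checks in escalated patients if the clinical team decides on them, and a little more tabulation from data already collected.

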3.5.1.8 Patient Diary

Patients will document daily reactions/symptoms and concomitant meds on the patient diary until cycle 13 (See [Appendix 10](#)). The patient diary will be reviewed at each clinic

visit. After cycle 13, patients will be asked to document their reactions/symptoms and concomitant medications on the log (See [Appendix 10](#)).

### 3.5.2 RESPONSE EVALUATION

Restaging studies (RECISTv1.1) with appropriate imaging studies and evaluation of disease-related symptoms will be performed at NIH after every 3 cycles x 4 (prior to cycle 4, 7, 10, 13) and then every 6 cycles (prior to cycle 19, 25, 31, etc).

- MRI of the abdomen/pelvis will be performed for restaging purposes. In the exceptional case of extraabdominal disease, the anatomical sites to be evaluated by MRI will be at discretion of the PI.
- FDG-PET will be performed prior to cycle 4, and then as clinically indicated. Patients  $\geq$  15 years of age will be given the option to consent for an early research FDG-PET (on day 3 to day 6) after initiation of therapy during cycle 1.
- CT of the chest will be performed for restaging purposes and if clinically indicated.

### 3.5.3 POST TREATMENT FOLLOW UP

#### 3.5.3.1 Off-Treatment Evaluation

Patients who have been taken off treatment for any of the criteria in [Section 3.6.1](#), will be monitored until resolution of toxicity, as clinically indicated, and efforts will be made to return to NIH at least once for Off-Treatment evaluation (at least 60 days after the last dose of vandetanib) for:

- Physical Examination with vital signs
- Laboratory Evaluation: CBC and differential, chemistry and liver function tests
- Toxicity assessment

Patients unable to return to NIH will be contacted by a member of the research team approximately 60 days after the last dose of investigational drug for an evaluation of toxicity.

Patients or the local medical provider will be contacted at least annually to obtain current status on patients who have completed the off treatment evaluation, until one of the off study criteria ([Section 3.6.2](#)) are met.

## 3.6 CRITERIA FOR REMOVAL FROM PROTOCOL THERAPY AND OFF STUDY CRITERIA

Prior to removal from study, effort must be made to have all subjects complete a safety visit approximately 60 days following the last dose of study therapy.

### 3.6.1 CRITERIA FOR REMOVAL FROM PROTOCOL THERAPY

Subjects will be removed from study therapy and followed until off-study criteria are met for any one of the following:

- Unacceptable toxicity (treatment limiting toxicity after two dose reductions, or treatment-limiting toxicity does not resolve to grade  $\leq$ 1 or baseline in  $\leq$  6 weeks of a drug free period). Patients who are removed from therapy for unacceptable toxicity will continue to undergo disease evaluations as per [Appendix 9](#) until they develop progressive disease.

- Concurrent use of agents that prolong the QTc: Vandetanib use must be discontinued if one of the QTc prolonging agents in Group 1 of [Appendix 7](#) is started.
- Progressive disease; clinical or radiographic evidence of progressive disease will discontinue vandetanib (see [Section 6.3](#)). If possible, tumor progression should be documented radiographically.
- Participant requests to be withdrawn from active therapy
- Positive pregnancy test
- Investigator discretion, which may include
  - The development of a concurrent serious medical condition that might preclude or contraindicate the further administration of vandetanib.
  - It is deemed in the best interest of the patient, and the reasons for discontinuation of vandetanib should be noted in the patient's medical record.
  - Serious protocol violation, such as non-compliance, as determined by the Principal Investigator.
- Death

### 3.6.2 OFF-STUDY CRITERIA

Subjects will be removed from study for any of the following criteria:

- Patient or guardian withdrawal of consent. Reasons must be noted on the patient's medical record.
- Lost to follow up after three documented attempts to contact patient/family/local referring physician.
- Death

**Note:** Minors are to be retained on the study at least until they reach the age of majority if possible and can be consented for the future use of their specimens and data. If you are enrolling minors, you need to leave them on study until they reach age 18 and can be consented for the future use of their specimens and data. If this consent is not obtained, samples and data may not be used in this study or future research unless the reason for removal is loss to follow up (for which a waiver has been requested in section [10.6.1](#)) or death (as these samples would no longer fall under human subjects' protections).

Overall survival is an endpoint on this trial. Patients will remain on this trial to be monitored for this endpoint.

